8.3.2 Time to CR or CRi with adequate blood count recovery

Time to CR or CRi with adequate blood count recovery is defined as the time from randomization to CR or CRi with adequate blood count recovery within 93 days after start of chemotherapy whichever occurs first. Patients without experiencing CR, CRi with adequate blood count recovery will be censored according to the following events:

- Patients experiencing induction failure will be censored at maximum follow-up (i.e. date of FPFV to date of LPLV used for the analysis).

The **date of last adequate response assessment** is the date of the last response assessment other than unknown before an event or a censoring reason occurred. In this case the last response evaluation date at that assessment will be used.

Table 8-2 Censoring rules for time to CR or CRi with adequate blood count recovery

Situation		Start-date	End-date	Outcome
A	CR or CRi with adequate blood count recovery within 93 days after start of chemotherapy	Date of randomization	Date of first onset of CR or CRi with adequate blood count recovery within 93 after start of treatment (before cut-off date)	Event
B	Induction failure	Date of randomization	At maximum follow-up (i.e. FPFV to LPLV used for the analysis) (before cut-off date)	Censor

8.3.3 Disease Free survival (DFS)

DFS is defined as the time from CR or CRi with adequate blood count recovery to relapse or death due to any cause. Patient who did not relapse nor died will be censored at the last adequate response assessment before cut-off date. DFS will be analyzed for patients who achieved CR or CRi with adequate blood count recovery within 93 days after start of chemotherapy.

Discontinuation due to lack of efficacy or failure to meet continuation criteria (collected on the ‘End of treatment’ and ‘End of post treatment follow up’ disposition pages without supporting documentation of relapse as per IWG criteria for AML [[Cheson et al 2003](#), [ELN 2017](#) / [Döhner et al 2017](#)]) will not be considered relapse for DFS derivation.

DFS will be estimated using the Kaplan-Meier method. The median DFS along with 95% confidence intervals will be presented by treatment group. The stratified Cox regression will be used to estimate the HR of DFS, along with 95% confidence interval.

Table 8-3 Censoring rules for DFS analysis

Situation		Start date	End Date	Outcome
A	Relapse from CR or CRi with adequate blood count recovery or death due to any reason	Date of first occurrence of CR or CRi with adequate blood count recovery	Date of Relapse from CR or CRi with adequate blood count recovery or death due to any reason	Event
B	No Relapse from CR or CRi with adequate blood count recovery nor death due to any reason	Date of first occurrence of CR or CRi with adequate blood count recovery within 93 days after start of treatment	Date of last adequate assessment	Censored

Situation	Start date	End Date	Outcome
C New anticancer therapy given/HSCT prior to relapse from CR or CRi with adequate blood count recovery or death	Date of first occurrence of CR or CRi with adequate blood count recovery	Date of Relapse from CR or CRi with adequate blood count recovery or death due to any reason	Event

8.3.4 Cumulative Incidence of Relapse (CIR)

Cumulative Incidence of Relapse (CIR) is defined for patients with CR or CRi with adequate blood count recovery within 93 days after start of chemotherapy and is time from achieving the CR or CRi with adequate blood count recovery until the onset of relapse from CR or CRi with adequate blood recovery. Patients without relapse are censored at the last adequate response assessment. Patients who died without relapse are counted as a competing cause of failure.

Table 8-4 Censoring rules for CIR analysis

Situation	Start date	End Date	Outcome
A Relapse from CR or CRi with adequate blood count recovery	Date of first occurrence of CR or CRi with adequate blood count recovery within 93 days after start of treatment	Date of Relapse from CR or CRi with adequate blood count recovery	Event of interest
B Death without relapse	Date of first occurrence of CR or CRi with adequate blood count recovery within 93 days after start of treatment	Death date	Competing event, censored
C No Relapse from CR or CRi with adequate blood count recovery	Date of first occurrence of CR or CRi with adequate blood count recovery within 93 days after start of treatment	Date of last adequate assessment	Censored
D Treatment discontinuation due to 'Lack of efficacy' or 'failure to meet continuation criteria' without documented relapse, i.e. clinical relapse based on investigator claim	Date of first occurrence of CR or CRi with adequate blood count recovery within 93 days after start of treatment	Date of last adequate assessment	Censored
E New anticancer therapy given/HSCT prior to relapse from CR or CRi with adequate blood count recovery	Date of first occurrence of CR or CRi with adequate blood count recovery within 93 days after start of treatment	Date of Relapse from CR or CRi with adequate blood count recovery or death due to any reason	Event of interest

Cumulative Incidence of Relapse (CIR) will be estimated using the Kaplan-Meier method. The median CIR along with 95% confidence intervals will be presented by treatment group. The stratified Cox regression will be used to estimate the HR of CIR, along with 95% confidence interval.

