To compare DFS, as well as the Cumulative Incidence of Relapse (CIR) and Cumulative Incidence of Death (CID) in the two treatment groups.	DFS, as measured from the date of first CR or CRi with adequate blood count recovery to relapse or death from any cause, whichever occurs first. CIR is defined for patients with CR or CRi with adequate blood count recovery: time from achieving CR or CRi with adequate blood count recovery until onset of relapse. Patients without relapse are censored at the last adequate response assessment. Patients who died without relapse are counted as a competing cause of failure. CID is defined for patients with CR or CRi with adequate blood count recovery: time from achieving CR or CRi with adequate blood count recovery until death. Patients who did not die are censored at the last contact date. Patients who relapsed are counted as a competing cause of failure.	Refer to Section 10.5.2.1
To compare the time to CR or CRi with adequate blood count recovery in the two treatment groups.	Number of days from date of randomization to first documented CR or CRi with adequate blood count recovery.	Refer to Section 10.5.2.1
To compare the time to neutrophil recovery in the two treatment groups.	Number of days from the first day of a chemotherapy cycle to first day neutrophils $\geq 0.5 \times 10^9/L$. Number of days from day 1 of commencing induction therapy to first day neutrophils $\geq 1.0 \times 10^9/L$.	Refer to Section 10.5.2.2

Objective	Endpoint	Analysis
To compare the time to platelet recovery in the two treatment groups.	Number of days from the first day of a chemotherapy cycle to first day platelets $\geq 50 \times 10^9/L$. Number of days from day 1 of commencing induction therapy to first day platelets $\geq 100 \times 10^9/L$.	
To assess the safety and tolerability of midostaurin in combination with chemotherapy and as monotherapy during post-consolidation.	Frequency/severity of AEs, and laboratory abnormalities.	Refer to Section 10.5.3
To further characterize the pharmacokinetics of midostaurin, CGP52421 and CGP62221.	Plasma concentrations and pharmacokinetic parameters for midostaurin, CGP52421 and CGP62221.	Refer to Section 10.5.4
To assess the impact of midostaurin on health related quality of life and AML symptom reduction.	Change from baseline score for each time point for the FACT-Leu and the EQ5D-5L (visual analogue scale (VAS)) by treatment arm.	Refer to Section 10.5.5

[REDACTED]	[REDACTED]	[REDACTED]

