10.5.2 Other secondary efficacy objectives

10.5.2.1 CR/CRi rate, Time to CR or CRi with adequate blood count recovery, Disease Free survival (DFS), Cumulative Incidence of Relapse (CIR) and Cumulative Incidence of Death (CID)

Other secondary efficacy variables include CR or CRi with adequate blood count recovery rate, DFS, CIR and CID. The assessment of these endpoints will be based on the IWG criteria for AML ([Cheson et al 2003](#), [ELN 2017 / Döhner et al 2017](#)) as per investigator assessment.

CR/CRi with adequate blood count recovery rate will be analyzed using Cochran-Mantel-Haenszel test based on strata at randomization. Estimated CR/CRi rate along with corresponding 95% confidence intervals will be presented by stratum and overall, and by treatment group.

Time to CR or CRi with adequate blood count recovery is defined as the time from randomization to CR or CRi with adequate blood count recovery whichever occurs first. Patients without experiencing CR, CRi with adequate blood count recovery will be censored according to the following events:

- Patients experiencing induction failure will be censored at maximum follow-up (i.e. date of FPFV to date of LPLV used for the analysis).
- Patients not experiencing induction failure and who did not die (any cause) will be censored at their last adequate response assessment date which is different from “unknown” or “not done”.

DFS is defined as the time from CR or CRi with adequate blood count recovery to relapse or death due to any cause. Patient who did not relapse nor die will be censored at the last adequate response assessment.

DFS will be estimated using the Kaplan-Meier method. The median DFS along with 95% confidence intervals will be presented by treatment group. The stratified Cox regression will be used to estimate the HR of DFS, along with 95% confidence interval.

Cumulative Incidence of Relapse (CIR) is defined for patients with CR or CRi with adequate blood count recovery and is time from achieving the CR or CRi with adequate blood count recovery until the onset of relapse from CR or CRi with adequate blood recovery. Patients without relapse are censored at the last adequate response assessment. Patients who died without relapse are counted as a competing cause of failure.

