Cumulative Incidence of Relapse (CIR) will be estimated using the Kaplan-Meier method. The median CIR along with 95% confidence intervals will be presented by treatment group. The stratified Cox regression will be used to estimate the HR of CIR, along with 95% confidence interval.

Cumulative Incidence of Death (CID) is defined for all patients achieving CR or CRi with adequate blood count recovery measured from the date of achievement of CR or CRi until the date of death due to any reason. Patients not known to have died are censored on the last contact date. Patients who experienced relapse are counted as a competing cause of failure.

CID will be estimated using the Kaplan-Meier method. The median CID along with 95% confidence intervals will be presented by treatment group. The stratified Cox regression will be used to estimate the HR of CID, along with 95% confidence interval.

The rate of CR/CRi with adequate blood count recovery will be analyzed based on the FAS. However, DFS, Cumulative Incidence of Relapse (CIR) and Cumulative Incidence of Death (CID) will be analyzed based on data from responders (CR or CRi with adequate blood count recovery) in the FAS. Assessment of relapse from CR or CRi with adequate blood count recovery, DFS, CIR and CID will not consider whether a patient received HSCT.

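### CIR and CID are defined with competing causes of failure but estimated by Kaplan-Meier with those events censored, and the SAP's CIR and CID tables do not fully match the definitions

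*SAP*

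**What the plan says.** **Definitions.** Protocol 10.5.2.1 says of CIR: "Patients who died without relapse are counted as a competing cause of failure". It says of CID: "Patients who experienced relapse are counted as a competing cause of failure". Protocol Table 3-1 and the objectives table in SAP section 2 agree on CID: "Patients who relapsed are counted as a competing cause of failure". SAP 8.3.4 repeats the CIR definition. SAP 8.3.5 narrows the CID one: only a relapse not followed by death is competing.

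**Estimation.** Protocol 10.5.2.1 and SAP 8.3.4 and 8.3.5 specify Kaplan-Meier for both endpoints ("Cumulative Incidence of Relapse (CIR) will be estimated using the Kaplan-Meier method"; "CID will be estimated using the Kaplan-Meier method"), with medians ("The median CIR along with 95% confidence intervals will be presented by treatment group") and a stratified Cox hazard ratio. Neither document names a cumulative incidence estimator.

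**Coding.** Row B of SAP Tables 8-4 and 8-5 gives the competing event the outcome "Competing event, censored". The word censored is attached to competing events only in these SAP tables; the protocol does not say how they enter the Kaplan-Meier estimate. Table 8-4 row E covers HSCT or new anticancer therapy before relapse. It has the end date "Date of Relapse from CR or CRi with adequate blood count recovery or death due to any reason" and is scored as an event of interest. In Table 8-5, rows A and D count any death as an event.

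**Status.** SAP 8.3 makes these endpoints descriptive, with 95% CIs and no p-values. SAP 3.8.5 adds subgroup forest plots of their hazard ratios. SAP section 1 says the decisions on the final analysis followed unblinding. SAP section 11 declares no change from the protocol.

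**The concern.** Cumulative incidence is the probability that a given event happens first, in the presence of the other. Kaplan-Meier with the competing event censored treats the removed patients as still able to have the event later. The result is always at least as high as the cumulative incidence, and higher once any competing event has occurred. The output would not be the quantity its label names. If deaths in remission differed between arms, 1-KM would show a difference in CIR even where the true incidences were equal.

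The tables add two problems of their own. Row E of Table 8-4 puts a death in remission after HSCT into the event count, while row B makes the same patient a competing case. HSCT is built into the design, so such patients are expected. In Table 8-5, a patient who relapses and later dies fits the event rows, while three other places in the documents make that relapse a competing event. Two programmers could follow the SAP faithfully and report different results.

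**Working it through.** The plan states no CIR or CID rate, so there is no figure to reproduce. The rates below are assumptions.

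**1. Size of the Kaplan-Meier excess.** Assume constant cause-specific hazards, relapse r = 40% and death in remission d = 5, 10, 15 or 20% at 24 months.

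- Total hazard: L = -ln(1 - r - d)/24 per month. Relapse hazard h1 = L·r/(r+d); death-in-remission hazard h2 = L·d/(r+d).
- Cumulative incidence at t months: CIR = r/(r+d)·(1 - exp(-Lt)); CID = d/(r+d)·(1 - exp(-Lt)).
- 1-KM with the competing event censored: 1 - exp(-h1·t) for CIR; 1 - exp(-h2·t) for CID (first event counted).

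Example with d = 10%, t = 12: 24L = -ln(0.50) = 0.6931, so 12L = 0.3466, 12h1 = 0.2773 and 12h2 = 0.0693. CIR = 0.8 × 0.2929 = 23.4% against 1-KM 24.2%. CID = 0.2 × 0.2929 = 5.9% against 1-KM 6.7%. The excess is 0.8 points in each.

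Excess of 1-KM, in percentage points, for d = 5/10/15/20%:

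| Time | CIR | CID |
|---|---|---|
| 12 months | 0.4/0.8/1.3/1.8 | 0.4/0.8/1.3/1.9 |
| 16 months | 0.6/1.3/2.1/3.0 | 0.7/1.4/2.3/3.2 |
| 24 months | 1.2/2.6/4.1/5.7 | 1.4/2.9/4.6/6.3 |

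**2. Which row of the table applies.** Protocol Amendment 1 (08-Jun-2018) records that no patient had been enrolled. SAP section 1 dates the futility stop to 23-Sep-2019 and says most patients left the study within the following weeks. That interval is about 15.5 months, and time from remission is shorter. The 12- and 16-month rows are therefore the relevant ones for most patients. A minority stayed on treatment for longer.

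**3. Cross-check on rates quoted in the protocol.** Protocol 1.1 cites post-HSCT 2-year relapse of 16% and 30% with leukemia-free survival of 71% and 58%.

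- 24h1 = -ln(0.71) × 16/29 = 0.1890, so 1-KM = 17.2% against 16.0%.
- 24h1 = -ln(0.58) × 30/42 = 0.3891, so 1-KM = 32.2% against 30.0%.

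The excess is 1.2 to 2.2 points at 2 years.

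**4. Medians.** With the rates of step 1, the Kaplan-Meier median for CIR is ln2/h1 = 31.3/30.0/28.6/27.2 months, against 33.2/34.0/35.0/36.3 for the cumulative incidence. CID levels off at d/(r+d) = 11/20/27/33% and so has no median, yet ln2/h2 gives 250/120/76/54 months. All of these lie beyond most patients' follow-up.

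**5. Table 8-4 row E.** Its end-date cell is word for word that of DFS Table 8-3 row C. The situation in the DFS row includes death; the situation in row E does not. Carry-over from the DFS table is an inference, but a well-supported one. If a fraction f of deaths in remission is counted as events, 1-KM becomes 1 - exp(-(h1 + f·h2)t). With f = 0.5 and the rates of step 3, the 2-year figures are 23.3% and 37.3%, against 16.0% and 30.0%. The hazard ratio shifts too. An assumed relapse HR of 0.70, with no effect on death in remission, becomes (0.70·h1 + f·h2)/(h1 + f·h2) = 0.72 to 0.76 for f = 0.5 with the rates of step 1.

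**6. Table 8-5.** Under a first-event reading, relapse ends follow-up for CID whatever happens next. That agrees with protocol Table 3-1, protocol 10.5.2.1 and SAP section 2, and step 1 gives the size. Under the literal reading, a relapsed patient who later dies is an event at death, while one still alive is censored at relapse. Censoring then depends on the future. A simulation with 30% relapse and 12% death in remission at 2 years, assumed median survival after relapse of 6 or 12 months and follow-up of 1 to 4 years gives 33.5% or 28.3%. That is neither death in remission (12.0%) nor all-cause death from remission (32.8% or 26.7%).

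**The case against.** The strongest reply is that this is small. The endpoints are descriptive, restricted to responders, and belong to a trial already stopped for futility. That stands, and it limits the point.

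A reader might quote the 24-month excess of up to 6.3 points, or predict that a meaningless CID median will be published. The documents do not support either for most patients: follow-up is too short, and the medians may simply not be reached.

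It can also be said that row E is a slip, since row B and the text of 8.3.4 already assign death without relapse to the competing event, and that a first-event reading reconciles Table 8-5. Both replies are fair. The row E and literal Table 8-5 figures are worst cases that arise only if those rows are programmed as worded. But the SAP states no order of precedence between rows, so the ambiguity remains.

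Finally, Kaplan-Meier is specified in the protocol, and replacing it after unblinding is a departure. That is a reason to declare the change and keep the Kaplan-Meier output. It does not make 1-KM a cumulative incidence.

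**Conclusion.** The plan is wrong as written on this point, with limited effect. Competing-risk definitions are paired with an estimator that ignores the competing risk. Under the assumed rates the reported incidence is too high by about 0.4 to 1.9 points at 12 months and 0.6 to 3.2 at 16 months. It would reach 1.2 to 6.3 points only at 24 months. These sizes rest on constant hazards and assumed rates; the direction does not.

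Table 8-4 row E contradicts row B and the CIR definition. SAP 8.3.5 and Table 8-5 differ from the CID definition given in three other places, and the rule that would reconcile them is not stated.

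A reader might infer that the Cox hazard ratios are invalid. Censoring competing events gives a legitimate cause-specific hazard ratio, so that inference fails for the estimator itself. The hazard ratios are distorted only if row E, or the literal Table 8-5, is programmed. Nor do the trial's main results depend on this: EFS, OS and DFS are untouched.

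**What to change.** - Estimate CIR and CID by the Aalen-Johansen cumulative incidence function. Report incidence with 95% CI at fixed times within the available follow-up, in place of medians.
- Keep the protocol's Kaplan-Meier output as a supplement, labelled as censoring competing events.
- In Table 8-4 row E, delete the reference to death from the end date, so that death without relapse falls under row B.
- In SAP 8.3.5 and Table 8-5, make every relapse a competing event at its date, so that rows A and D apply only to death without prior relapse.
- Label the stratified Cox hazard ratios, including those in the forest plots, as cause-specific.
- Declare the change from protocol 10.5.2.1 in SAP section 11 as made after unblinding.

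The cost is SAP wording and a small amount of reprogramming, with no new data. The price in credibility is a declared post-unblinding departure, which showing the protocol analysis alongside keeps small.

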8.3.5 Cumulative Incidence of Death (CID)

Cumulative Incidence of Death (CID) is defined for all patients achieving CR or CRi with adequate blood count recovery within 93 days after start of chemotherapy and is measured from

the date of achievement of CR or CRi with adequate blood count recovery until the date of death due to any reason. Patients not known to have died are censored on the last contact date. Patients who experienced relapse without death are counted as a competing cause of failure.

Table 8-5 Censoring rules for CID analysis

Situation	Start date	End Date	Outcome
A Death due to any reason	Date of first occurrence of CR or CRi with adequate blood count recovery within 93 days after start of treatment	Death date	Event of interest
B Relapse without death	Date of first occurrence of CR or CRi with adequate blood count recovery within 93 days after start of treatment	Relapse date	Competing event, censored
C No death	Date of first occurrence of CR or CRi with adequate blood count recovery within 93 days after start of treatment	Date of last contact date	Censored
D New anticancer therapy given/HSCT prior to deaths	Date of first occurrence of CR or CRi with adequate blood count recovery within 93 days after start of treatment	death due to any reason	Event of interest

CID will be estimated using the Kaplan-Meier method. The median CID along with 95% confidence intervals will be presented by treatment group. The stratified Cox regression will be used to estimate the HR of CID, along with 95% confidence interval.

8.3.6 Measurable Residual Disease (MRD) by flowcytometry (LAIP approach)

8.3.6.1 MRD status

MRD status will be reported for all patients as best response of MRD assessment outcome. Thus, patients who reached at least once MRD- will have their MRD status as negative. If all MRD assessment are positive or undetermined then MRD status will be reported as such.

It is acknowledged that for patients who failed induction therapy, no MRD assessment should be available. MRD status of these patients will be reported as ‘not done due to induction failure’. If patient failed induction therapy but have MRD assessment evaluated, MRD status will be reported as is in the analysis. Of note, some patients reached CR or CRi with adequate blood count recovery after 93 days after start of treatment and are considered to have failed induction therapy.

Patients completing successfully induction therapy (i.e. CR or CRi with adequate blood count recovery within 93 days after start of treatment) without MRD assessment will be reported as ‘missing’ for their status of MRD. This will be the case also for consolidation and post-consolidation until CR or CRi with adequate blood count recovery is not maintained.

The percentage of patients with MRD negative/positive/undetermined/missing (irrespective of investigator response assessment as per ELN criteria) be summarized along with exact 95% CI by treatment group and by treatment phase (i.e. Induction (I and II), consolidation and post-consolidation). If sufficient number of patients entering post consolidation, comparisons of the MRD levels between the end of the consolidation phase during the post-consolidation phase will be performed by treatment groups. Status of MRD for patients moving to HSCT and re-entering post-consolidation will be summarized prior and post HSCT.

In addition, the percentage of patients with CR and MRD-, CR with MRD+, CR and undetermined status of MRD and CR with missing MRD data will be reported by treatment groups. Similarly for CRi with adequate blood count recovery and other response categories (CRi without adequate blood count recovery, PR, etc.). Only CR and CRi with adequate blood count recovery will be counted within 93 days after start of chemotherapy will be considered.

Moreover, the kinetics of MRD levels (quantitative) will be displayed in terms of boxplot by over time for each treatment phase.

